## 8.2. Setting

The study population will consist of patients with a diagnosis of hormone receptor-positive/human epidermal growth factor receptor 2-negative mBC who initiated a who initiated PB+FUL and CCI

The USON includes 1,200 affiliated physicians operating in over 470 sites of care across states and treats approximately 1 million US cancer patients annually.

**Figure 1** presents a graphical depiction of the study time periods, which are as follows:

- Study observation period: 01 February 2016 – 30 June 2020.\*
- Study identification period: 01 February 2016 – 31 December 2019.
- Index date: The date of initiation with PB+FUL or CCI during the study identification period. For PB+FUL, the date of the first administration of either drug will be used.
- Baseline: Assessment will be done for the data collected at the closest date prior to index within 30 days of index (in absolute value). Variables to be assessed at baseline are specified in **Table 2**.
- Prior medical history: Patients' available history in the iKnowMed (iKM) EHR will vary based on the length of disease and the time within the USON. The prior medical history period will end the day prior to the index date. Variables to be assessed with prior medical history are specified in **Table 2**.
- Follow-up: Patients will be followed through the end of the study observation period, date of last visit or date of death, whichever occurs first. For analysis, patients will have a potential of at least 6 months of follow-up duration; however, patients will have variable follow-up time periods, depending on their index dates and last contact dates.

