### 8.2.1. Inclusion criteria

Patients must meet all the following inclusion criteria to be eligible for inclusion in the study:

---

\* Data can be updated at a later time to extend the follow-up period through an amendment to refresh the data and revisit charts of patients who were alive at the end of the original study period.

- 1) Patients with a documented diagnosis of hormone receptor-positive (estrogen receptor-positive or progesterone receptor-positive), human epidermal growth factor receptor 2-negative mBC\*
- 2) Aged 18 years at initial recorded diagnosis of mBC
- 3) Initiated one of the following qualifying regimens within the USON during the study identification period:
  - a) PB+FUL as first-line (for primary and secondary objectives) or CCI [REDACTED]
  - CCI [REDACTED]
- 4) Received care at a USON site(s) utilizing the full EHR capacities of iKM at the time of treatment.
- 5) EHR data available from the USON site(s) where the patient received treatment are accessible for research purposes.
- 6) During the study observation period, patients observed with at least 2 visits† after the index date.

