### **8.2.2. Exclusion criteria**

Patients meeting any of the following criteria will not be included in the study:

- 1) Enrollment in an interventional clinical trial during the study observation period since clinical trial participants may have clinical scenarios that deviate from the population of interest.
- 2) Evidence of prior treatment with CDK 4/6 inhibitors (ribociclib or abemaciclib) in the metastatic setting.
- 3) Receipt of treatment indicated for another primary cancer during the study observation period or history of another primary cancer within the USON iKM EHR database.

---

\* Diagnosis of hormone receptor-positive/human epidermal growth factor receptor 2-negative breast cancer (BC) will be determined through a review of iKM's discrete diagnosis fields, which are populated during the routine course of care (International Classification of Diseases [ICD] codes will not be used). To identify patients with metastatic disease status, patients must have at least one of the following indicators: 1) receipt of a numbered LOT, 2) Stage IV disease, 3) Tumor, Node, Metastasis (TNM) staging with M value of 1, 4) record of location of metastatic disease or 5) current or prior disease status containing reference to metastatic disease.

† Visits are defined as physical encounters with the practice, detected by vital sign records. The second and third visits must be observed after the index date to demonstrate continuity of care. There is no required time span between the additional visits and the index date.

4) Initiated first treatment more than 120 days after metastatic date.

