## Palbociclib (IBRANCE)

## Study Number A5481128 NON-INTERVENTIONAL STUDY PROTOCOL

Protocol Version 2, August 30, 2021

				the proportion of patients with a duration less than or greater than/equal to 12 months.
Surgery	Chart review	Treatment characteristics	Medical history prior to index	The proportion of patients who had surgery prior to the index treatment.
Radiotherapy	Chart review	Treatment characteristics	Medical history prior to index	The proportion of patients who received radiation prior to the index treatment.
Index treatment regimen	iKM structured data + chart review	Eligibility criteria, Treatment characteristics	Study observation period	Patients' index treatment will be categorized based on the cohort descriptions in Section 8.1: PB+FUL CCI
Date of treatment initiation during the patient identification period (i.e., index date)	iKM structured data + chart review	Eligibility criteria, Treatment characteristics	Study observation period	The date of initiation with a PB+FUL or CCI during the study identification period. If the combination regimen consists of more than one drug with drugs given on different dates, the date of the first administration of any drug will be used. Patients who did not initiate a qualifying regimen during the patient identification period will be excluded from the study.
Treatment initiation by quarter	iKM structured data + chart review (derived)	Treatment characteristics	Study observation period	The proportion of patients who initiate treatment by quarter.
Index treatment end date(s)	iKM structured data + chart review	Treatment characteristics	Study observation period	Date of final treatment for each drug or regimen. It is possible that the patient's treatment stop date is not documented if the patient dies, is lost-to follow-up or is still on-therapy. The final treatment date, death date or end of study date will be used, whichever is earliest.
Index line of therapy (LOT)	iKM structured data + chart review (derived)	Treatment characteristics	Study observation period	LOT will be assigned based on the absolute chronologic order of regimens, based treatment start and stop dates. Specifically, first-line treatment designation will be assigned to the first treatment received after metastatic diagnosis. Line of therapy will advance with each subsequent regimen.

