Follow-up duration	iKM structured data, chart review + external sources (derived)	Clinical outcomes	Study observation period	The duration between index and last follow-up date. Findings will be summarized as the mean ( $\pm$ SD) and median (range) for all patients within the specified cohort. The number of patients with available data will be reported.
Vital status	iKM structured data, chart review + external sources (derived)	Clinical outcomes	Study observation period	Patients without a date of death recorded in iKM, LADMF, NDI or other commercial sources of death information used for the study will be assumed to be alive at the end of the study. Those with a date of death in available records will be flagged as deceased. Further information on the sources of death information is presented in Section 8.4 .
Overall survival (OS)	iKM structured data, chart	Clinical outcomes	Study observation period	OS will be defined as the interval (in weeks) between index treatment and the date of death (any cause) as documented in the iKM EHR database, LADMF, NDI and other

	review + external sources (derived)			commercial sources of death records that may be used for this study. Patients who did not die within the study observation period will be censored on the study end date or the last visit date available in the dataset, whichever occurred first. OS will be analyzed using the Kaplan-Meier method with 95% CIs, and summary tables of the number of events and censored patients 6, 12, 18, 24, 30, and 36 months.
Survival rate	iKM structured data, chart review + external sources (derived)	Clinical outcomes	Study observation period	Survival rates will be provided along with the Kaplan-Meier OS analyses described above as survival rates at 6, 12, 18, 24, 30, and 36 months.
Real-world progression-free survival (rwPFS)	iKM structured data, chart review + external sources (derived)	Clinical outcomes	Study observation period	The rwPFS will be measured from the initiation of the index treatment to the date of progression or date of death due to any cause, censoring patients who are still alive at the end of the study observation period and did not progress at the last visit date. The rwPFS will be estimated in weeks using the Kaplan-Meier method with 95% CIs, and summary tables of the number of events and censored patients at 6, 12, 18, 24, 30, and 36 months.

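### The PB+FUL clock starts at the first dose of either drug, with no limit on the wait for the second drug and no rule for late add-ons, so OS can include immortal time

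*Protocol*

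**What the plan says.** Protocol 8.2 (Setting) gives the index rule for the combination: "For PB+FUL, the date of the first administration of either drug will be used". SAP 2.1.1 repeats it. The index-date row of Protocol Table 2, repeated in SAP Table 1, foresees staggered starts. For a combination regimen "with drugs given on different dates, the date of the first administration of any drug will be used".

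Cohort entry depends on the regimen. Protocol 8.2.1 requires initiation of "PB+FUL as first-line (for primary and secondary objectives"), which means both drugs.

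Two other rules bear on the interval:

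- Protocol 8.2.2 excludes a patient on this ground: "Initiated first treatment more than 120 days after metastatic date". This runs from metastatic date to first treatment, not from first drug to second.
- In the line-of-therapy row of Table 2, "first-line treatment designation will be assigned to the first treatment received after metastatic diagnosis", and "Line of therapy will advance with each subsequent regimen". The row does not say whether adding a drug to an ongoing one makes a new regimen, or after how long.

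All six time-to-event endpoints in Protocol 8.7.3 (time to chemotherapy, rwDOT, TTNT, OS, rwTTP, rwPFS) run from index treatment. No landmark, delayed-entry or gap-based sensitivity analysis is planned.

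**The concern.** Membership of the PB+FUL cohort requires the second drug, but follow-up starts at the first. If the drugs start apart, membership depends on something that happens after time zero. A patient who dies before the second drug is never classed as PB+FUL; one who lives to receive it is, and the waiting time is credited to the combination. For OS this is immortal time.

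The other five endpoints are exposed less directly:

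- **TTNT and time to chemotherapy:** a patient who moves to another treatment before the second drug would not be first-line PB+FUL, so such events tend to be screened out.
- **rwDOT:** single-drug time is counted as time on the index regimen.
- **rwPFS and rwTTP:** a patient who dies in the gap is lost from the cohort. Progression documented in the gap could still be counted, because no rule excludes it.

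The same silence affects who is in the cohort. Two analysts applying the line-of-therapy row could place the same late adder in first line or in second line.

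**Working it through.** **Nothing to reproduce.** The plan gives no figure that depends on the index rule, and no distribution of the interval between drugs. What follows is an illustration.

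**Inputs from the documents**
- First-line PB+FUL cohort: N = 317 (Protocol Table 3).
- Range for the true median M: 9.5, 27.9 and 31.8 months, the PB+FUL median PFS values cited in Protocol section 6.

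**Assumed inputs, not in the documents**
- Share of late adders f: 5% to 30%.
- Gap g: 2 to 26 weeks, the same for all late adders, with no event possible in the gap. In months, g = weeks × 7 × 12 / 365.25, so 4, 13 and 26 weeks are 0.92, 2.99 and 5.98 months.
- Exponential times from the start of the combination.

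**Formula.** With λ = ln 2 / M,

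S(t) = (1 − f)·exp(−λt) + f·exp(−λ·max(t − g, 0)).

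For t > g this equals exp(−λt)·[1 + f(2^(g/M) − 1)], so

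shift in median = (M / ln 2) · ln[1 + f(2^(g/M) − 1)].

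**Worked case:** M = 9.5, f = 30%, g = 26 weeks.
- 2^(5.98/9.5) = 1.547.
- 1 + 0.30 × 0.547 = 1.164, and ln 1.164 = 0.152.
- 9.5 / 0.693 = 13.71, and 13.71 × 0.152 = 2.08 months.

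| f | g | Median shift, M = 9.5 (months) | Median shift, M = 27.9 (months) | 12-month estimate, M = 9.5 (points) | 12-month estimate, M = 27.9 (points) |
|---|---|---|---|---|---|
| 5% | 4 wk | +0.05 | +0.05 | +0.1 | +0.1 |
| 10% | 4 wk | +0.09 | +0.09 | +0.3 | +0.2 |
| 10% | 13 wk | +0.33 | +0.31 | +1.0 | +0.6 |
| 20% | 13 wk | +0.65 | +0.62 | +2.0 | +1.1 |
| 30% | 26 wk | +2.08 | +1.89 | +6.8 | +3.6 |

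At M = 31.8 the last row gives +1.88 months and +3.2 points.

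**Reading the table.** The shift is close to f × g (0.30 × 5.98 = 1.79 months in the last row) and changes little with M. It therefore gives a fair idea for OS too, where the no-event assumption holds by construction. For rwPFS and rwTTP it is an upper-end figure, because progression in the gap may be recorded.

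**For scale.** The 95% half-width of a survival proportion at N = 317 without censoring is 1.96·√(p(1 − p)/317): 5.4 points at p = 0.40 and 4.8 at p = 0.75. The bias is well inside sampling error when gaps are a few weeks. It becomes comparable only when long gaps are common.

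**Patients involved.** 5% to 30% of 317 is about 16 to 95.

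**The case against.** The strongest reply is that the line-of-therapy row already deals with late adders. Read naturally, a drug started alone is first-line treatment and a combination begun months later is a subsequent regimen, so the patient leaves the first-line cohort. Table 3 shows that lines were assigned in practice: 52 patients were removed at the sequencing step, and first-line (317) and second-line (78) PB+FUL are counted separately. The index-date row can also be read as only choosing a date within what is already one regimen.

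This stands in part. It makes the bias possible rather than certain. It does not remove it, because neither document says when an added drug makes a new regimen, and the rule applied at the sequencing step is not stated.

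Three further objections are sound:

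- A reader might infer that every endpoint is affected. Two of the eight, reasons for discontinuation and the proportion with documented progression, are not durations.
- A reader might infer that any comparison would favour PB+FUL. The comparator and its details are redacted, so the direction of a differential bias cannot be checked.
- Making the later start date the primary time zero is debatable. Protocol 8.9.1 says it cannot be determined whether oral therapies were dispensed or taken, and moving the index date also moves the baseline windows.

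**Conclusion.** The point holds as a gap in the definitions. Time zero is the first drug, membership needs both, and nothing bounds the interval or settles the line of a later add-on. Where such patients are kept as first-line PB+FUL, the interval is immortal time for OS and can push the other five time-to-event endpoints upward.

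The size is unknown because the gap distribution is not reported. Under the assumed shares and gaps it runs from less than 0.1 month to about 2 months on the median. The high end needs 30% late adders with six-month gaps and no events in the gap. The documents do not support saying that the estimates are biased by any particular amount. They do show that the plan, as written, could not tell a negligible bias from a material one.

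**What to change.** **Definition.** In Protocol 8.2, the index-date and line-of-therapy rows of Table 2, SAP 2.1.1 and the matching rows of SAP Table 1, state that the two drugs form one PB+FUL regimen only if both start within a fixed window (for example 30 days, matching the baseline window). Assign line and cohort for later add-ons by the regimen first started. This is an analysis classification only. Any remaining guaranteed interval is then at most the window; a 4-week gap in 30% of patients shifts the median by 0.28 month.

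**Reporting.** Tabulate the interval between the two start dates, and the number of patients outside the window.

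**Sensitivity analysis.** Repeat the time-to-event analyses with time zero at the later start date, or with delayed entry or a landmark. State that a palbociclib start may reflect prescription rather than intake.

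**Cost.** Revised wording and a re-derivation. Applying the current rule already requires comparing the two drugs' start dates, so no new abstraction should be needed. Protocol 8.7 calls for the protocol to be updated and resubmitted to the IRB if the SAP is modified, and Protocol 8.7.3 requires an amendment for additional analyses. Late adders beyond the window leave the 317-patient first-line cohort. In the illustration that is nobody if all gaps are 4 weeks or less, and up to about 95 patients if 30% have longer gaps. The loss is large only where the bias would be a real concern.

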### 8.2.1. Inclusion criteria

Patients must meet all the following inclusion criteria to be eligible for inclusion in the study:

---

\* Data can be updated at a later time to extend the follow-up period through an amendment to refresh the data and revisit charts of patients who were alive at the end of the original study period.

- 1) Patients with a documented diagnosis of hormone receptor-positive (estrogen receptor-positive or progesterone receptor-positive), human epidermal growth factor receptor 2-negative mBC\*
- 2) Aged 18 years at initial recorded diagnosis of mBC
- 3) Initiated one of the following qualifying regimens within the USON during the study identification period:
  - a) PB+FUL as first-line (for primary and secondary objectives) or CCI [REDACTED]
  - CCI [REDACTED]
- 4) Received care at a USON site(s) utilizing the full EHR capacities of iKM at the time of treatment.
- 5) EHR data available from the USON site(s) where the patient received treatment are accessible for research purposes.
- 6) During the study observation period, patients observed with at least 2 visits† after the index date.

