**Figure 1. Overview of study design**

\* Data can be updated at a later time to extend the follow-up period through an amendment to refresh the data and revisit charts of patients who were alive at the end of the original study period. The health information available for research purposes may vary in accordance with the data rights under agreements with physician practices. Therefore, data from some practices that are part of the USON may not be available for research purposes.

A phased approach to project execution is being undertaken for this study. First, a feasibility assessment has been performed based solely on structured data to describe demographic, clinical and treatment characteristics of all patients who meet the eligibility criteria defined in **Section 8.2**. Next, chart review was performed to verify patients' eligibility and capture additional details about eligible patients. The chart review sampling method is described in **Section 8.2.4**.

Study objectives are described in **Section 7**. The primary and secondary objectives will be assessed among patients who initiated first-line PB+FUL. **CCI** [REDACTED]

A complete list of study variables and their associated operational definition are presented in **Table 2**. The clinical endpoints to be evaluated for this study include:

- Time to chemotherapy
- Reasons for treatment discontinuation
- rwDOT
- TTNT
- Provider-documented progression
- rwTTP
- rwPFS
- OS

The complete analysis plan is presented in **Section 8.7**. Descriptive analyses will be conducted to evaluate demographic, clinical and treatment characteristics of the study population, stratified by pre-specified cohorts. Time-to-event outcomes will be assessed using the Kaplan-Meier method with 95% CIs and summary tables among those who initiated first-line PB+FUL. **CCI** [REDACTED]

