Additional visits	iKM structured data	Eligibility criteria	Follow-up	To capture a sample of patients with longitudinal records, patients will be required to have 2 records of either additional visits following the index date visit and/or a record of death prior to the end of the study follow-up period. Visits are defined as physical encounters with the practice, detected by vital sign records. There will be no distinction made, for purposes of inclusion, between patients that have an additional USON visit and those with a record of death. There is no minimum or maximum requirement on time from index date to these qualifying events.
Sex	iKM structured data +	Baseline characteristic	Prior medical history	Patients will be categorized as: Male Female

PFIZER CONFIDENTIAL

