### 8.7.3. Statistical methods

#### Description of study enrollment

To be included in the study patients must meet each of the inclusion criteria and none of the exclusion criteria listed in **Sections 8.2.1-8.2.2**. Counts of patients excluded for each criterion will be summarized.

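### Two follow-up rules for eligibility: criterion 6 needs 2 post-index visits, while the Additional visits row also accepts death; following criterion 6 would keep early deaths out of OS and rwPFS

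*Protocol*

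**What the plan says.** **Visits only.** Inclusion criterion 6 (Protocol 8.2.1; SAP 4.1) reads "During the study observation period, patients observed with at least 2 visits", counted after the index date. Its footnote defines a visit as a physical encounter detected through vital signs and adds: "The second and third visits must be observed after the index date to demonstrate continuity of care". A death record cannot satisfy this. The Table 3 label for the step (Protocol 8.5) likewise describes an exclusion for fewer than 2 post-index visits and does not mention death.

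**Visits or death.** The Additional visits row (Protocol Table 2; SAP Table 1) has the stated role of an eligibility criterion. It says "patients will be required to have 2 records of either additional visits following the index date visit and/or a record of death", and then that there will be "no distinction made, for purposes of inclusion, between patients that have an additional USON visit and those with a record of death".

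**Authority.** Each text has a claim. Protocol 8.7.3 (and SAP 7.2) admits patients by the criteria list: "To be included in the study patients must meet each of the inclusion criteria and none of the exclusion criteria listed in" Sections 8.2.1-8.2.2. Protocol 8.1 gives Table 2 the operational role: "A complete list of study variables and their associated operational definition are presented in" that table; Section 8.6 says much the same. No sentence ranks them.

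**Endpoints.** OS runs from index treatment to death from any cause, and rwPFS is "measured from the initiation of the index treatment to the date of progression or date of death due to any cause". Both are Kaplan-Meier estimates (Protocol 8.7.3; SAP 7.1) with no delayed entry or landmark.

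**The concern.** Two analysts working from these documents could build different cohorts. A patient with one post-index visit who then died is out under criterion 6 and in under the Additional visits row.

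The difference bears on survival. Under criterion 6, inclusion depends on surviving to a second post-index visit, so the time from index to that visit is free of deaths by design. OS still counts it as time at risk, and so does the death part of rwPFS. (A progression in that interval can still be counted, because the patient can survive it and go on to a second visit.) Early survival then tends to be overstated, and a larger cohort would not remove the error. The limitations in Protocol 8.9 do not mention it.

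**Working it through.** **1. The plan's own count.** Table 3 for PB+FUL, all lines: 840 − 47 = 793, then 793 − 10 = 783. Both figures reproduce. The number at stake at this step is therefore 10, or 10/793 = 1.3%.

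**2. The rules side by side.**

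| Patient | Criterion 6 and Table 3 label | Row, read as two records of any kind | Row, read as two visits or a death |
|---|---|---|---|
| 2 or more later visits | in | in | in |
| 1 later visit, then death | out | in | in |
| No later visit, then death | out | out | in |
| Fewer than 2 later visits, alive | out | out | out |

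The rules differ only on early deaths, and the row has two possible readings for a death with no later visit.

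**3. Size if criterion 6 was applied.** Inputs: 10 excluded (Table 3); final first-line PB+FUL cohort 317 (Table 3). Let d be the number of the 10 who belong in that cohort and died before time t. If those deaths came before any retained patient was censored, restoring them multiplies the Kaplan-Meier estimate by 317/(317 + d). Hence

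overstatement = reported S(t) × d/(317 + d), which is no more than d/(317 + d) under that condition.

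| d | d/(317 + d) | Points |
|---|---|---|
| 0 | 0 | 0 |
| 1 | 1/318 | 0.3 |
| 4 | 4/321 | 1.2 |
| 7 | 7/324 | 2.2 |
| 10 | 10/327 | 3.1 |

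At an assumed reported S(t) of 0.90, d = 4 gives 0.90 × 4/321 = 1.1 points and d = 10 gives 0.90 × 10/327 = 2.8 points.

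**4. A plausible d.** The documents do not give it. Assume that each of the 10 had the same line mix and later attrition as the 783 retained: 317/783 = 0.405, so 10 × 0.405 is about 4. Under a binomial with that probability, 1 to 7 patients covers 98%, and the chance that all 10 belong is about 0.0001. This says how many belong in the cohort, not how many died.

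**5. The condition matters.** If the deaths fall after some retained patients have been censored, each weighs more. For illustration, assume that 100 of the 317 are already censored, with no earlier deaths. Then d = 4 gives 4/221 = 1.8 points and d = 10 gives 10/227 = 4.4 points.

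**6. Scale.** The 95% CI half-width at n = 317 without censoring is 1.96 × √(S(1 − S)/317). This is 3.3, 2.4 and 1.5 points at an assumed S of 0.90, 0.95 and 0.98.

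**7. Check on the remedy.** Admitting these patients only if they died selects on the outcome. Assume that all 10 belong in the cohort, 5 died early, 5 are alive at t, and S among the 317 is 0.90. Adding the deaths only gives 0.90 × 317/322 = 88.6025%. Keeping all 10 gives (0.90 × 317 + 5)/327 = 88.7768%. The deaths-only estimate is 0.17 points too low. At S = 0.70 the same sum gives 0.48 points.

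**The case against.** The strongest reply is that the documents already contain the harmless reading. Table 2 holds the operational definitions, the Additional visits row is the only eligibility text that addresses death, and it treats a later visit and a death alike. Criterion 6 could then be shorthand for the row. If that was coded with any death qualifying, early deaths are retained and the bias is largely or wholly absent. This is a fair reading, but it is not stated, and both the enrolment text and the Table 3 label point the other way. The mismatch stands, and so does the need to say which rule was applied.

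A reader might infer that early deaths have in fact been removed and that the survival estimates are biased. The documents do not support that. The only sign of the visits-only rule in use is a short label in a feasibility table, and some or all of the 10 may simply have left the network. Some may also have index dates before 01 February 2016, since Table 3 applies that cut-off later.

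A reader might also take d/(317 + d) as a ceiling. It is not one, because it requires that the deaths precede all censoring among retained patients.

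The remaining objections concern weight, and they stand. Few patients are affected, OS and rwPFS are secondary descriptive estimates, and the 1.2-point figure is below every half-width in step 6. Exclusion counts by criterion are already planned, though not the vital status of those excluded.

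**Conclusion.** This is an internal inconsistency of minor severity, present in the current text of both documents. That the rules conflict is certain. That any result is biased is conditional on criterion 6 having been followed and on some of the 10 having died early.

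On those conditions the direction is known: early survival is overstated. The size runs from 0 to up to about 1.2 points on the pro rata assumption with all 4 dying early, and up to 3.1 points if all 10 belong in the first-line cohort and died early. These figures hold for deaths before any censoring among the 317 and are not an unconditional limit. The point merits action because it is cheap to settle before the outcomes analyses, which Protocol Table 1 places in December 2021 and January 2022.

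**What to change.** 1. State one rule in the same words in criterion 6, its footnote and the Additional visits row in both documents, and in the Table 3 label: a death after index satisfies the follow-up requirement, whatever the number of visits.
2. State which rule was coded. Report the 10 excluded patients by line, index date (before or after 01 February 2016) and vital status, alongside the exclusion counts already planned in Protocol 8.7.3 and SAP 7.2.
3. Include early deaths whose eligibility is confirmed by chart in OS, and in rwPFS as deaths. Because this admits poorly followed patients only if they die (step 7), add a sensitivity analysis that also keeps the eligible living patients among the 10, censored at last contact.

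**Cost.** The change needs a protocol and SAP update with IRB resubmission (footnote to Protocol 8.7). It also needs a few chart verifications: the 10 were removed before chart selection, Section 8.6.1 requires a CRF for each included patient, and chart review closed in December 2020. Eligibility cannot be assumed, since first-line PB+FUL fell from 488 at feasibility to 317. Early survival may look slightly less favourable.
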